4.4. Sample Size

The study is expected to enroll 3 cohorts of 3 subjects and additional 3 subjects at the OBD for a total of 12 subjects. The maximum of subjects to be enrolled is 18. This sample size consideration is consistent with the sample size of other study with similar design.

4.5. Randomization, Stratification, and Blinding

This is an open label study, so no randomization is implemented.

4.6. Analysis Set

4.6.1. Safety Set (SS)

The SS will include all subjects who receive DTX101. Subjects who have a partial dose will be considered as being treated and included in the SS. The SS is used to tabulate and list all of the safety endpoints.

4.6.2. As Treated Set (ATS)

The ATS will include all subjects who receive any amount of DTX101. Subjects will be treated by the dose they receive. Subjects who receive a partial dose will be adjusted to the nearest candidate dose (see [Table 3-1](#)) based on the dose they actually received. ATS will be used for all efficacy analyses and bCRM modelling.

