In nonclinical studies by Nathwani et al, rhesus macaques inoculated with scAAV8-FIX at a dose of 2.0×10^{11} GC/kg expressed a peak of 35% to 40% of normal FIX levels in serum by Day 15 [Nathwani 2011b]. It must be noted that later correction of dosage methods suggested these animals actually received a dose of 2.0×10^{12} GC/kg [Nathwani 2011a]. In comparison, when administered to human patients in a Phase I dose-escalation clinical trial, 2.0×10^{12} GC/kg resulted in sustained average levels of only $5.1 \pm 1.7\%$ of normal FIX activity [Nathwani 2011a; Nathwani 2014]. Based on the corrected dosing, this represents approximately a 10-fold difference in transduction and expression levels between nonhuman primates and humans.

When considering a clinical dosing rationale, in light of the available comparison data between mice, nonhuman primates and humans, it seems reasonable to consider a 100-fold increase in dose from mice to humans to achieve similar target levels of FIX. Therefore, the proposed MED range for human dosing with a target peak expression level of 20% would fall between 1.6×10^{12} and 5.0×10^{12} GC/kg. The proposed initial clinical dose of DTX101 is 1.6×10^{12} GC/kg, 100-fold above the lower end of the MED range in the mouse. Dose escalation would follow at either 3.0×10^{12} GC/kg or 5.0×10^{12} GC/kg. The final dose, 1.0×10^{13} GC/kg, is consistent with a half log increase over the upper end of the proposed human MED range.

A starting dose of 1.6×10^{12} GC/kg has a safety margin of 3-fold versus the no observed adverse effect level (NOAEL) determined in the formal GLP toxicology study (Study 2371-002; refer to section Section 4.4.1.2 of the IB). The primary safety finding from this study was the prolongation of aPTT times that correlated with supraphysiological FIX expression and activity levels. The highest dose tested, 5.0×10^{13} GC/kg, resulted in a peak average prolongation of aPTT of 63% at Day 15. This prolongation began to resolve by Day 29, being 43% at Day 29 and 15% by Day 90. Mice in this dose group (5.0×10^{13} GC/kg) were expressing supraphysiological levels of FIX at more than 2500% of normal.

Although prolongation of aPTT was present, these animals exhibited no related clinical signs or complications. Lower doses of DTX101 resulted in minimal to moderate increases of aPTT that were often not statistically significant.

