3.2.4 Safety Stopping Criteria

Enrollment will be suspended and the study will be discussed with regulators if, at any time during the study, any of the following occur:

- Death of a subject, at any time, that is considered related to DTX101 by the investigator,
- Fivefold increase in baseline (predose, Day 0) ALT within 8 weeks after vector infusion that is considered related to DTX101 by the investigator,
- Grade 2 toxicity develops that persists for more than 7 days and is considered related to DTX101 by the investigator,
- At least Grade 3 toxicity develops, including an infusion-related reaction \geq Grade 3, that is considered related to DTX101 by the investigator, or
- Occurrence of a malignancy, at any point after administration of vector, that is considered related to DTX101 by the investigator.

Abnormal clinically significant laboratory values (hematology, coagulation panel, and clinical chemistry) as assessed by the investigator will be considered AEs. Laboratory values that meet any of the above criteria will result in the suspension of the study.

Any event that meets the above criteria will be reported immediately as outlined in [Section 9.1.2.2](#), and the appropriate pages of the electronic case report form (eCRF) must be completed. Enrollment and dosing will be temporarily suspended until the situation can be assessed and risks to subjects mitigated. If study enrollment is suspended, all subjects who have been enrolled will remain in the study and will continue to be monitored through their completion or withdrawal from the study.

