10.5.3.1 Adverse Events

All statistical analyses of safety outcomes will be descriptive. The incidence of AEs and TEAEs will be summarized for each dosing cohort by severity and relationship to study product. Serious AEs will be presented for each dosing cohort by relationship to study product. Summary tables will present incidence estimates and individual event rates by system organ class as well as within each system organ class. Subjects experiencing an event

more than once with varying severity will be counted only once, in the maximum severity within each system organ class and preferred term. For incidence of relationship to study product, subjects will be counted only once, in the category of the strongest relationship to study product within each system organ class and preferred term.

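### SAP 4.6.2 rounds partial infusions to the nearest candidate dose for the bCRM: a near-zero infusion without a DLT counts as a full Dose 1, and a DLT that cuts short an assigned Dose 2-4 can be charged to a lower dose

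*SAP*

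**What the plan says.** SAP 4.6.2 (As Treated Set) makes four statements that act together:

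- Entry: "The ATS will include all subjects who receive any amount of DTX101". No minimum exposure is given.
- Principle: "Subjects will be treated by the dose they receive".
- Partial doses: "Subjects who receive a partial dose will be adjusted to the nearest candidate dose", meaning the Table 3-1 doses. Whether nearness is judged on the arithmetic or the log scale is not stated.
- Use: "ATS will be used for all efficacy analyses and bCRM modelling".

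There is no exception for a partial dose caused by a DLT. SAP 4.6.1 keeps partial-dose subjects in the Safety Set and states no dose reassignment.

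A DLT is a related AE of Grade 3 or higher (Protocol 10.5.1, SAP 3.1.2). The stopping criteria in Protocol 3.2.4 foresee such an event during infusion: "At least Grade 3 toxicity develops, including an infusion-related reaction". Protocol 10.5.3.1 tabulates safety by cohort: "The incidence of AEs and TEAEs will be summarized for each dosing cohort by severity and relationship to study product".

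**The concern.** In the bCRM the dose label is the covariate and the DLT or FIX response is the outcome. The rounding rule can corrupt the label in two ways.

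**(a) Rounding up at the bottom.** Dose 1 is the lowest category, so any smaller amount becomes a full Dose 1. A subject given 1% of Dose 1 who has no event is evidence about almost no exposure. The model reads him as evidence that Dose 1 is tolerated and ineffective. This also departs from the SAP's own as-treated principle.

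**(b) The outcome sets its own label.** If a related Grade 3 infusion reaction stops the infusion, the DLT determines how much went in and therefore the dose it is charged to. The accounting is one-sided. Subjects in the same cohort who passed through that exposure without reacting stay at the assigned dose, while the one who reacted moves down.

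At stake are the next-cohort dose and the OBD, a primary objective decided on about 12 to 18 subjects. The same DLT may also appear at one dose in the by-cohort AE tables and at another in the model.

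**Working it through.** **Inputs from the documents.** Doses 1.6, 3.0, 5.0 and 10 (×10^12 GC/kg; SAP Table 3-1). Model logit p = 3 + βx with β ~ Exp(1), and selection by smallest Euclidean distance (SAP 3.1.1). MTD and MED rates 25% and 90% (SAP 3.1.2). Expected enrolment (SAP 4.4): 3×3 + 3 = 12, which reproduces.

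**Step 1: where the label changes.** Cut-off = midpoint between adjacent doses ÷ assigned dose.

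Arithmetic midpoints: (1.6+3.0)/2 = 2.3; (3.0+5.0)/2 = 4.0; (5.0+10)/2 = 7.5. Log-scale midpoints: √(1.6×3.0) = 2.19; √(3.0×5.0) = 3.87; √(5.0×10) = 7.07.

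| Assigned | Becomes | Arithmetic: below | Log: below |
|---|---|---|---|
| Dose 4 | Dose 3 | 7.5/10 = 75% | 70.7% |
| Dose 4 | Dose 2 | 4.0/10 = 40% | 38.7% |
| Dose 4 | Dose 1 | 2.3/10 = 23% | 21.9% |
| Dose 3 | Dose 2 | 4.0/5.0 = 80% | 77.5% |
| Dose 3 | Dose 1 | 2.3/5.0 = 46% | 43.8% |
| Dose 2 | Dose 1 | 2.3/3.0 = 76.7% | 73.0% |
| Dose 1 | never moves | – | – |

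The unstated scale matters: 75% of Dose 2 is 2.25, which is Dose 1 on the arithmetic scale and Dose 2 on the log scale. One percent of any dose counts as Dose 1.

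**Step 2: assumptions for the model effect.** The SAP does not give the skeleton (the prior probabilities behind x). Assumed toxicity skeletons: S1 (.05,.10,.15,.25), S2 (.05,.10,.20,.35), S3 (.02,.05,.10,.20), S4 (.10,.20,.30,.45). Assumed efficacy skeletons: (.2,.4,.6,.8), (.3,.5,.7,.9), (.1,.25,.5,.75). I set x = logit(skeleton) − 3, integrated the posterior over a grid of β, treated toxicity and efficacy as independent, used 0.25 and 0.90 as the desired rates, and took the DLT subject as a non-responder.

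**Step 3: near-zero Dose 1 subject, no DLT, no response.** Counted (n = 3) versus not counted (n = 2):

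- P(DLT at Dose 1), no DLTs in the other two: 0.048-0.064 versus 0.072-0.096.
- P(efficacy at Dose 1), one responder in the other two: 0.394-0.416 versus 0.554-0.580.
- Selected dose, over 0-2 DLTs × 0-2 responders in the other two (4×3×3×3 = 108 scenarios): it differs in 14, each time higher when the subject is counted. All 14 have at least one DLT in the other two. With none (36 scenarios) the selection never changes.

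**Step 4: one DLT among three subjects assigned Dose 4**, after 0/3 at Dose 1 and 0/3 at Dose 3. Posterior P(DLT at Dose 4):

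| Skeleton | Kept at Dose 4 | To Dose 3 | To Dose 2 | To Dose 1 |
|---|---|---|---|---|
| S1 | 0.200 | 0.229 | 0.249 | 0.280 |
| S2 | 0.224 | 0.266 | 0.306 | 0.340 |
| S3 | 0.209 | 0.245 | 0.276 | 0.313 |
| S4 | 0.227 | 0.267 | 0.297 | 0.339 |

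The dose nearest 25% stays Dose 4 except when the DLT moves to Dose 1; it then becomes Dose 3 under S2-S4. Over all responder counts (4×3×4×4×3 = 576 scenarios) the minimum-distance dose changes in 0 (to Dose 3), 1 (to Dose 2) and 48 (to Dose 1).

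**Step 5: one DLT among three subjects assigned Dose 3**, after 0/3 at Dose 1. P(DLT at Dose 3) is 0.246-0.269 kept, 0.270-0.310 moved to Dose 2, and 0.307-0.353 moved to Dose 1. The dose nearest 25% is Dose 3 under all four skeletons if kept, Dose 2 under two of four if moved to Dose 2, and Dose 2 under all four if moved to Dose 1. Over all responder counts (4×3×4×3 = 144 scenarios) the minimum-distance dose changes in 7 (to Dose 2) and 28 (to Dose 1). Every change in Steps 4 and 5 is to a lower dose.

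**The case against.** The best defence is that as-treated attribution is a legitimate pre-specified choice. A Grade 3 reaction after 20% of Dose 4 occurred at 2.0×10^12 GC/kg, close to Dose 1 exposure. The model is also not the only safeguard: a related Grade 3 infusion reaction suspends enrolment and dosing (Protocol 3.2.4), prompts an ad hoc DSMC meeting (Protocol 9.3), and the DSMC sees tables and listings beside the bCRM output (SAP 12). The documents give no rate of partial infusions, so the situation may never arise. In most scenarios above the selected dose does not move.

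All of that stands as a limit on size. It does not rescue the rule. As-treated attribution cannot justify rounding a near-zero infusion up to 1.6×10^12 GC/kg. Nor does it deal with a label chosen by the outcome: in Step 5, moving the DLT to Dose 1 turns 0/3 there into 1/4, although the two completers at Dose 3 passed through the same exposure without a DLT and add nothing at Dose 1.

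A reader might infer more than the documents support:

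- That every DLT that stops an infusion is charged to an unassigned dose. It cannot happen at Dose 1 or when the infusion stops late.
- That moving a DLT down hides toxicity at the higher dose. The estimate rises at every dose.
- That relabelling by itself makes Dose 4 cross a 25% MTD line. SAP 3.1.2 defines the MTD as the dose nearest 25%, and under S1 that remains Dose 4 throughout. Protocol 10.5.1 speaks of reaching 25%; under S1 only the move to Dose 1 (0.280) does so.
- That a truncated Dose 1 infusion generally drives escalation. It changed the selection only in some patterns, all with a DLT elsewhere in the cohort.

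**Conclusion.** The point holds in both parts. The label cut-offs and the rounding up of near-zero infusions follow directly from the SAP text and Table 3-1. Part (a) is the less cautious direction: estimated toxicity and efficacy at Dose 1 are both too low, and the selected dose is higher in 14 of 108 scenarios. Part (b) errs towards caution, but biases the MTD and OBD and can disagree with the by-cohort AE tables. The selected dose changes in 28 of 144 (19%) and 48 of 576 (8%) scenarios when the DLT moves to Dose 1, and rarely or never for smaller moves.

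These counts describe a grid of equally weighted scenarios and are not probabilities. They rest on assumed skeletons, independent margins and assumed desired rates. The SAP should be changed because cohorts have three subjects and one label carries weight, but the effect is conditional on a partial infusion occurring.

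**What to change.** In SAP 4.6.2, for the bCRM only:

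1. Count a subject with a DLT at the assigned cohort dose, whatever fraction was infused.
2. Treat a subject without a DLT who received less than a pre-specified fraction of the assigned dose as not evaluable for the bCRM, instead of rounding to a candidate dose.
3. For a DLT subject below that fraction, leave the FIX outcome out of the efficacy likelihood, so that he contributes to the toxicity margin only.
4. Report the OBD under the as-rounded rule as a sensitivity analysis, stating the distance scale used.

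Entering the actual GC/kg would not fit, because x in SAP 3.1.1 is a nominal value tied to each candidate dose and an unplanned amount has none.

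Cost: one fewer FIX-evaluable subject if a partial infusion occurs, and a stated rule for a subject with toxicity data only in a joint model. Items 1 and 2 together let a DLT count at any exposure while a non-event needs the minimum. That is an asymmetry, but a cautious one, and it should be stated openly. The SAP should also say how a cohort left with two evaluable subjects proceeds, since Protocol 7.2 does not replace subjects who withdraw after dosing and is silent on non-evaluable ones. No new data are needed: dose, stop time and volume are already recorded (Protocol 6.3.1).

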4.6.3. Per-Protocol Set (PPS)

The PPS will consist of all subjects who receive DTX101, have no significant protocol deviations, and have at least 60% of scheduled FIX activity samples collected during the study (52 weeks). Protocol deviations, whether significant or not, will be identified prior to database lock. PPS is used as a supplement to the ATS analysis.

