10.5.8 Interim Analysis

An interim analysis will be conducted when the last subject dosed completes Week 6 of the study. The purpose of this interim analysis is to determine FIX activity in all cohorts to determine the OBD of DTX101 and provide an initial safety and efficacy assessment of DTX101. Results and their dissemination will be at the sponsor's discretion. Any interim analyses conducted will not bias the conduct of the study. A detailed plan for the analysis of the safety and efficacy data will be presented in the SAP.

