7.2. Drug Exposure

The duration of study participation will be summarized by dosage for all subjects. The duration of study participation (days) is calculated as the date of the last visit (as recorded on the Study Completion/Early Withdrawal page) minus date of the Day 0 visit plus 1. If the date of the last visit on the Study Completion/Early Withdrawal page is missing, or if a subject is lost to follow-up, the latest available visit date will be used. The duration of study participation for each subject will also be presented in a listing.

The SS will be used for all analyses defined above.

8. Efficacy Analysis

The primary efficacy endpoint is defined as the change from baseline in FIX activity at Week 6 as determined by aPTT. The EDA, through descriptive statistics and graphic method, will be performed on the primary efficacy endpoint.

The secondary efficacy endpoints include: ABR; and the annualized and average weekly FIX replacement therapy. All secondary efficacy endpoints will be presented in a listing at the scheduled time points for each subject and will be summarized by dosage at scheduled time points. No formal statistical inference will be performed for the secondary efficacy endpoints.

All efficacy analyses will be conducted on the ATS. Additionally, sensitivity analyses for the primary efficacy endpoint will be performed by utilizing the PPS; additional sensitivity analyses will be performed if necessary.

9. Safety Analysis

Safety evaluations will be based on the incidence, severity, type of AEs, clinically significant changes or abnormalities in the subject's vital signs, and clinical laboratory results.

All safety analyses will be conducted on the SS.

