9.11. Factor IX genotyping

A listing will be provided for the subjects who provide the samples for genotyping.

10. Quality of Life (QoL) Analyses

Two questionnaires, EQ-5D-5L and Haem-A-QoL, will be collected at baseline, week 24, 36, 48, and 52. For EQ-5D-5L Listings will be presented for each questionnaire.

11. Pharmacodynamics

FIX activity, as measured by aPTT will be presented in a listing for each scheduled time points for each subject. FIX activity will be summarized by dosage at each scheduled time point. It will also be presented in a figure along with cell-mediated immune response for each subject. The association between FIX activity and dose will be evaluated by a linear mixed-effects regression model adjusted for potential confounders.

12. Statistical considerations for Data Safety Monitoring Committee (DSMC) meeting

DSMC members will meet after week 6 data from all subjects of a cohort is available. Dosage recommendation computed through bCRM along with necessary tables/listings/figures (denoted by * in the table of contents) will be prepared and presented.

13. Interim Analysis

An interim analysis will be conducted after week 6 FIX activity results are available for all enrolled subjects. All tables/listings/figures for the full analysis will be produced for interim analysis.

14. References

Braun TM. The bivariate continual reassessment method: extending the CRM to phase I trials of two competing outcomes. *Control Clin Trial.* 2002;23:240-56.

White GC 2nd, Rosendaal F, Aledort LM, et al. Definitions in hemophilia. Recommendation of the scientific subcommittee on factor VIII and factor IX of the scientific and standardization committee of the International Society on Thrombosis and Haemostasis.

Tessella 2005. Simulation Test Results. Bivariate Continuous Reassessment Method.

15. Appendices

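### The Per-Protocol Set is defined by 52-week FIX sampling but supports a Week 6 endpoint, so entry depends on attendance after the outcome, and no interim version of the rule is given

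*SAP*

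**What the plan says.** SAP 4.6.3 builds the Per-Protocol Set (PPS) from subjects who received DTX101, had no significant protocol deviation, and "have at least 60% of scheduled FIX activity samples collected during the study (52 weeks"). It adds that "Protocol deviations, whether significant or not, will be identified prior to database lock". It describes the set as a supplement to the analysis of the As Treated Set (ATS).

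SAP 8 names one analysis for the PPS: "sensitivity analyses for the primary efficacy endpoint will be performed by utilizing the PPS". The endpoint concerned is a Week 6 quantity: "The primary efficacy endpoint is defined as the change from baseline in FIX activity at Week 6 as determined by aPTT".

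SAP 4.6.2 gives the main role to the other set: "ATS will be used for all efficacy analyses and bCRM modelling".

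On timing, SAP 13 says that "An interim analysis will be conducted after week 6 FIX activity results are available for all enrolled subjects" and that "All tables/listings/figures for the full analysis will be produced for interim analysis". Protocol 10.5.8 gives part of the purpose of that interim as "to determine FIX activity in all cohorts to determine the OBD of DTX101". Neither document says how the 60% is to be counted for a subject who has not finished 52 weeks.

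**The concern.** A per-protocol set for a Week 6 endpoint should turn on what happened up to Week 6. This one turns mainly on whether the subject kept attending afterwards. Someone with a sound Week 6 value who leaves the study some months later is removed from the Week 6 sensitivity analysis. Adverse events and noncompliance are among the withdrawal reasons in Protocol 7.1, so such removals need not be random. Dosed subjects are not replaced (Protocol 7.2). In a cohort of three, one removal takes a third of the cohort.

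The interim makes the mismatch more visible. It falls when the last subject has only Week 6 data, yet the PPS outputs are due then as well. A reader comparing PPS and ATS results by dose would be looking at a set shaped by calendar time since dosing, not by protocol adherence.

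At stake is the usefulness of the one named robustness check on the primary efficacy endpoint.

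**Working it through.** **The plan's own figure.** SAP 4.4 expects 3 cohorts of 3 plus 3 more at the optimal biological dose (OBD): 3 × 3 + 3 = 12, with a maximum of 18. The SAP gives no expected PPS size and no power calculation to reproduce.

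**Scheduled FIX samples.** The FIX row of Protocol Table 15-1 covers screening, Day 0, Weeks 2, 4, 6, 8, 10 and 12 (6 samples), Weeks 16 to 48 every 4 weeks (9 samples) and Week 52 (1 sample). Post-dose total: 6 + 9 + 1 = 16. With Day 0 it is 17, and with screening as well 18. The synopsis instead says FIX is sampled at each visit. If that adds the 11 visits of Table 15-2, the post-dose total is 16 + 11 = 27.

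**The 60% mark.** Samples needed = 0.60 × total, rounded up. The last column assumes perfect attendance.

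| Samples counted | Total | Needed | Held by Week 6 | Mark first reached |
|---|---|---|---|---|
| Table 15-1, post-dose | 16 | 9.6 → 10 | 3 (18.8%) | Week 28 |
| plus Day 0 | 17 | 10.2 → 11 | 4 (23.5%) | Week 28 |
| plus Day 0 and screening | 18 | 10.8 → 11 | 5 (27.8%) | Week 24 |
| Post-dose, Table 15-2 visits added | 27 | 16.2 → 17 | 9 (33.3%) | Week 12 |

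On every count, six or more samples taken after Week 6 are needed.

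**Who is dropped.** Take a subject with a valid Week 6 value who attends through Week 16, then withdraws and gives a FIX sample at the early-withdrawal visit. Post-dose samples: 6 + 1 + 1 = 8.
- 8/16 = 50%
- with Day 0, 9/17 = 53%
- with Day 0 and screening, 10/18 = 56%

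All fall short. On the 27-sample count the same subject passes even without the withdrawal sample: (7 + 11)/27 = 67%. There the exclusion falls on earlier leavers. A subject who leaves after Week 8 has 4 + 8 + 1 = 13 samples, and 13/27 = 48%.

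**The interim.** SAP 3.1.2 sets at least 7 days between subjects in a cohort and at least 42 days from the last dose of one cohort to the first dose of the next. With four cohorts of 3, dosing falls on days 0, 7, 14; 56, 63, 70; 112, 119, 126; 168, 175, 182. The interim is then day 182 + 42 = 224. Follow-up in weeks is 32, 31, 30; 24, 23, 22; 16, 15, 14; 8, 7, 6. Three subjects, all in Cohort 1 and so at Dose 1, have passed Week 28. A fourth, the first of Cohort 2, has reached Week 24.

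The table gives the number who could qualify, with perfect attendance and no significant deviations. The 14- and 56-day intervals are an assumption, used to show slower accrual.

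| Scenario | Interim day | 16 count | 18 count | 27 count |
|---|---|---|---|---|
| 12 subjects, 7/42 days | 224 | 3/12 | 4/12 | 9/12 |
| 12 subjects, last 3 added without the 42-day gap | 189 | 0/12 | 3/12 | 6/12 |
| 18 subjects, 7/42 days | 336 | 9/18 | 10/18 | 15/18 |
| 12 subjects, 14/56 days | 322 | 6/12 | 6/12 | 9/12 |
| 18 subjects, 14/56 days | 490 | 12/18 | 12/18 | 15/18 |

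The last three subjects dosed contribute none in any row. In the 12-subject plan these are the three added at the OBD.

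**Would moving the percentage to Week 6 be enough?** 60% of the samples through Week 6 is 2 of 3 post-dose, or 3 of 5 with Day 0 and screening. Weeks 2 and 4 alone give 2 of 3, so the Week 6 sample has to be required by name.

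**The case against.** Much of the case on the other side stands.

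- **Dose selection.** A reader might infer that the PPS could distort the choice of OBD, because the interim serves that choice. The documents rule this out. SAP 4.6.2 puts the dose-finding model and all efficacy analyses on the ATS. The primary efficacy analysis is descriptive, and SAP 11 lists and plots FIX for every subject, so nobody's data are hidden.
- **An almost empty set.** A reader might infer that hardly anyone qualifies at the interim. That holds only near minimum intervals with about 12 subjects on the Table 15-1 counts. More subjects, slower accrual or the synopsis count all raise the number. If 60% meant samples due to date, every attending subject could qualify. If it meant 52 completed weeks, nobody would in the minimum-interval cases (longest follow-up 32 weeks with 12 subjects, 48 with 18). The SAP does not choose between these readings.
- **Members without a Week 6 value.** They do no harm. SAP 4.1 sets the change to missing, imputes nothing, and summarises only subjects with both values.
- **Later leavers.** A subject who leaves after Week 20 passes at (8 + 1 + 2)/18 = 61% if baseline and early-withdrawal samples count. Week 16 is the safer example.
- **Washout.** A reader might infer that the PPS ignores washout failures. That cannot be said, because SAP 4.6.4 refers to a list in Appendix C whose content is not in the text available.
- **Other checks.** SAP 8 allows further sensitivity analyses if necessary, though it specifies none.

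What the objection does not remove is the mismatch itself. On every count in the table, data through Week 6 cannot admit anyone.

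**Conclusion.** The point holds as a fault of definition in a supplementary analysis. The PPS rule covers 52 weeks, the analysis it serves ends at Week 6, and membership therefore selects on attendance after the outcome. This affects the Week 6 sensitivity analysis at the interim and at the final analysis. At the final analysis the set need not be small, but it is still selected in this way.

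The size at the interim depends on conditions. Under Table 15-1 at minimum intervals, 3–4 of 12 or 9–10 of 18 subjects would qualify, and none from the last cohort. These figures assume perfect attendance, no significant deviations, a 60% rule counted against the full 52-week schedule, and a 42-day gap before the last three subjects.

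The OBD and the main efficacy results are not affected. The change is worth making because it is cheap, not because the dose decision is at risk.

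**What to change.** In SAP 4.6.3, define the PPS for the Week 6 endpoint as subjects who received DTX101, had no significant deviation through Week 6, and have a FIX sample within the Week 6 visit window. This definition can be applied to every dosed subject at the interim, so no separate interim rule is needed for this endpoint.

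Do not remove subjects from the set for on-demand FIX use before that sample. Protocol 3.2.3.2 allows such use at any time. Subjects with low expression are plausibly the ones more likely to bleed and be treated, so excluding them could raise the apparent Week 6 FIX level. Flag the use, list it by dose, and keep the ATS as the main analysis.

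Keep the 60% rule, if wanted, only for 52-week FIX summaries at the final analysis. State which visits form its denominator: whether screening, Day 0, early-withdrawal and Table 15-2 visits count. The synopsis and Table 15-1 should be reconciled on which visits carry a FIX sample.

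The cost is one SAP sentence and a small extra listing. No new data are needed.
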